Study Protocol

Title:

Effects of Taurine Supplementation on Repetitive Sprint Performance and Exhaustion Time in College Students Under High-Temperature and High-Humidity Conditions

Protocol ID:

No. 2021A43

Date:

January 9, 2025

1. Background

High-temperature and high-humidity environments (defined as ambient temperature \geq 35°C and relative humidity \geq 60%) adversely affect sports performance by increasing the body's heat load and impairing thermoregulation. These conditions lead to earlier fatigue, reduced performance, and increased physiological strain. Recovery after exhaustion is critical in such conditions for enhancing subsequent performance.

Taurine, a sulfur-containing amino acid, has shown promise in enhancing sports performance, improving calcium regulation in muscles, reducing oxidative stress, and mitigating fatigue under extreme environmental conditions. Previous studies have highlighted taurine's benefits, but the effects of different taurine doses in repetitive sprint (RS) exercises after exhaustive exercise in high-temperature and high-humidity conditions remain unclear. This study aims to investigate these effects in college students.

2. Objectives

Primary Objective:

To examine the effects of acute pre-exercise taurine supplementation at different doses (6g, 4g, 1g) on RS performance and endurance following exhaustive exercise in high-temperature and high-humidity environments.

Secondary Objectives:

- To analyze the impact of taurine on physiological indicators, such as heart rate (HR) and blood lactate (BLA).
- To measure subjective sensations using the rating of perceived exertion (RPE).
- To evaluate recovery performance through reverse vertical jump height.

3. Study Design

Design:

- Single-blind, randomized, crossover-controlled experimental design.
- Four groups: High-dose taurine (6g), Medium-dose taurine (4g), Low-dose taurine (1g), Placebo (0g).
- Each subject participated in four trials, one for each group.

Environment:

• Temperature maintained at 32±1°C and relative humidity ≥60%, using a heating system (SAWO, Finland) and humidification system (BELIN, China).

Participants:

- 16 college students (8 male, 8 female) from Capital University of Physical Education and Sports.
- Inclusion Criteria:
 - 1. Aged 18–28 years.
 - 2. No exercise-related risk as indicated by the PAR-Q questionnaire.
 - 3. No taurine-based supplementation in the past month.

Experimental Process:

- Pre-exercise taurine/placebo ingestion (6g, 4g, 1g, or placebo).
- RS test (6 sprints, 10 seconds each, with 10-second recovery intervals).
- Measurements: Peak Power (PP), Mean Power (MP), Fatigue Index (FI), HR, BLA, RPE, and exhaustion time (ET).

4. Experimental Procedure

- 1. Warm-Up:
 - o 5-minute steady-state cycling at 100W.
 - o Measurement of reverse vertical jump height.
- 2. Exhaustive Exercise Test:

- Cycling test to exhaustion, starting at 50W and increasing by 50W every 3 minutes at 60 RPM.
- Exhaustion determined by cadence drop or inability to maintain resistance.

3. Rest and Recovery:

 20-minute recovery period with periodic measurements of HR, RPE, and BLA.

4. Repetitive Sprint Test (RS):

 Six maximal sprints (10 seconds each) with resistance set at 7.5% of body weight.

5. Measurements

- Sports Performance Indicators: PP, MP, FI (recorded for each sprint).
- Endurance and Recovery Indicators: ET, reverse vertical jump height.
- **Physiological Indicators**: HR and BLA (monitored pre-, post-exercise, and during recovery).
- **Subjective Indicators**: RPE assessed at pre-defined intervals.

6. Statistical Analysis

- Data analyzed using SPSS 27.0.
- Normality tested using the Shapiro-Wilk test.
- Repeated measures ANOVA (group × time) for performance indicators.
- Paired-samples t-tests for pre- and post-test comparisons.
- Significance level set at P<0.05.

7. Ethical Considerations

- Study approved by the Institutional Ethical Committee of Capital University of Physical Education and Sports, Beijing, China (No. 2021A43).
- Informed consent obtained from all participants.

Statistical Analysis Plan

Title:

Statistical Analysis Plan for the Effects of Taurine Supplementation on RS Performance in High-Temperature and High-Humidity Environments

Protocol ID:

No. 2021A43

Date:

January 9, 2025

1. Objectives

- Analyze the effects of different taurine doses on RS performance metrics (PP, MP, FI).
- Assess endurance and recovery indicators (ET, reverse vertical jump height).
- Investigate physiological responses (HR, BLA) and subjective fatigue (RPE).

2. Statistical Software

• SPSS Version 27.0.

3. Data Analysis Methods

- 1. Descriptive Statistics:
 - \circ Means \pm standard deviations calculated for all variables.
- 2. Normality Test:
 - Shapiro-Wilk test to check for normal distribution.
- 3. Primary Analysis:
 - Repeated measures ANOVA for group × time interaction effects on PP, MP, FI, HR, BLA, and RPE.
- 4. Secondary Analysis:
 - Paired-samples t-tests for reverse vertical jump pre- and post-exercise comparisons.

o One-way ANOVA for ET across groups.

5. Effect Sizes:

o Partial eta-squared (η^2 partial): 0.01 (small), 0.06 (medium), 0.14 (large).

4. Data Presentation

- Line graphs for repeated measures (PP, MP, FI, HR, BLA, RPE).
- Bar charts for pre- and post-test comparisons (reverse vertical jump).

5. Significance Criteria

• Statistical significance set at P<0.05.

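### The four-visit crossover has no visit term in any planned analysis and states no sequence scheme, so a visit trend would cost precision in the dose comparisons of exhaustion time and of session-level outcomes

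*Combined protocol and SAP*

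**What the plan says.** Protocol section 3 (Design) gives a "Single-blind, randomized, crossover-controlled experimental design" and adds "Each subject participated in four trials, one for each group". The participants are "16 college students (8 male, 8 female"). Every session takes place in heat: "Temperature maintained at 32±1°C and relative humidity ≥60" per cent. Each session contains a ride to exhaustion, a 20-minute recovery and six maximal sprints (Protocol section 4). No Latin square, counterbalancing, familiarisation session or interval between sessions is mentioned.

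Protocol section 6 plans "Repeated measures ANOVA (group × time) for performance indicators". SAP section 3 names as primary "Repeated measures ANOVA for group × time interaction effects on PP, MP, FI, HR, BLA, and RPE". Its secondary analyses are paired t-tests of jump height before and after exercise, and a one-way ANOVA for ET.

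The time factor lies within a session. Protocol section 5 has "PP, MP, FI (recorded for each sprint") and "HR and BLA (monitored pre-, post-exercise, and during recovery"). It therefore does not stand for visit 1 to 4, and visit number enters no analysis.

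**The concern.** Outcomes such as ET, peak power and RPE depend on effort and familiarity. Over four exhausting sessions in heat, with no stated familiarisation, a drift from the first visit to the fourth is credible. In a crossover each participant's doses are compared across visits, so drift that is not modelled adds to the within-person error. If orders were drawn independently for each person, the doses would also differ by chance in their average visit number.

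With 16 participants and no sample-size calculation in the documents, precision is what this design has to offer. The protocol's primary objective concerns the effect of dose on sprint performance and endurance. That effect is read from the overall dose comparison and from ET, the two places where a visit trend does harm.

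**Working it through.** The plan gives no power, SD or effect size, so there is no figure of its own to reproduce.

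**Inputs from the documents.** 16 participants, 4 visits, 4 doses, significance level 0.05.

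**Assumptions.** One value per session; within-person SD = 1; a linear trend of b within-person SD per visit; participant included in the model; independent random orders; two-sided test; true dose-placebo difference of 1.0 SD.

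**1. Error variance without a visit term.** The visit effects are 0, b, 2b and 3b, with mean 1.5b. Their sum of squares about the mean is (2.25 + 0.25 + 0.25 + 2.25)b² = 5b², so their variance is 5b²/3 = 1.667b². The error variance is 1 + 1.667b², and

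Var(dose − placebo) = 2(1 + 1.667b²)/16.

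Residual degrees of freedom are 64 − 16 − 3 = 45. Power is from the noncentral t distribution.

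| b per visit | First to fourth visit | Error variance | SE of difference | Power |
|---|---|---|---|---|
| 0 | 0 | 1.00 | 0.354 | 79% |
| 0.1 | 0.3 | 1.02 | 0.356 | 78% |
| 0.25 | 0.75 | 1.10 | 0.372 | 75% |
| 0.5 | 1.5 | 1.42 | 0.421 | 64% |
| 1.0 | 3.0 | 2.67 | 0.577 | 40% |

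**2. Chance imbalance.** Between two doses, mean visit number differs with SD √(2 × 1.667/16) = 0.456 visits. At b = 0.5 this is 0.456 × 0.5 = 0.228 SD. It is already contained in the SE above: 0.354² + 0.228² = 0.125 + 0.052 = 0.177 = 0.421². It is not a second loss to be added.

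**3. Simulation of the dose F test** (1,500 runs per setting; dose effects 0, 0, 0.5 and 1 SD). With random orders and no visit term, power was 0.77, 0.57 and 0.33 at a total drift of 0, 1.5 and 3 SD. With the visit term it was about 0.72 to 0.75 throughout. Type I error without the term stayed at 0.043 to 0.055.

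**4. Balanced orders, visit not modelled.** The imbalance vanishes but the error stays inflated. Type I error fell to 0.019 and 0.008 at a total drift of 1 and 2 SD, and power to 0.67 and 0.41. With balanced orders and a visit term, power stayed at about 0.75 to 0.78.

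**5. The named interaction test.** Simulated data for 16 people × 4 doses × 6 sprints were analysed after adding a session-wide shift of 0, 1 or 3 SD per visit. The group × time F statistic did not change. A constant added to all time points of a session drops out of both the interaction and its error term.

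**6. Price of the visit term.** Residual degrees of freedom go from 45 to 42. With balanced orders and no trend, power goes from 79.0% to 78.9%. With unrestricted random orders, visit and dose are not orthogonal: the median SE is about 0.363 and power about 77%.

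**The case against.** The strongest reply is that the SAP's named primary test is the group × time interaction, from which a session-wide shift cancels exactly. The same holds for the pre/post jump differences. This stands. A reader might infer that every planned outcome analysis loses power; the analyses as named do not support that. The loss falls on ET and on dose main effects or pairwise dose comparisons of session-level values. A visit effect that altered the profile within a session could reach the interaction, but nothing in the documents allows that to be sized.

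Second, the protocol says only that the crossover is randomised. A reader might infer that the orders were unbalanced, but silence does not show it, and 16 participants would fit a balanced allocation. If orders were balanced, the chance imbalance disappears and the error inflation remains.

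Third, the trend size is assumed. The largest value used means 3 within-person SDs over four visits, and small trends cost little. This also stands.

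Fourth, a reader might take the plan to produce false dose effects. Under random orders the estimate is unbiased over randomisations and type I error is held; under balanced orders without a visit term the test is conservative.

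Finally, the past-tense wording in Protocol section 3 suggests that the sessions may be over. A new allocation would then be unavailable, and the visit term alone recovers less than the balanced design would: at 0.25 SD per visit, about 77% against 75%.

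**Conclusion.** The concern holds for ET and for the overall and pairwise dose comparisons of PP, MP, FI, HR, BLA and RPE. It is a matter of precision. The loss is negligible at about 0.1 SD per visit, modest at 0.25 and material from about 0.5. These sizes rest on a linear trend, independent random orders, one value per session and a participant term in the model.

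For ET, a one-way ANOVA run literally, without a participant term, is a separate and larger fault: simulated power was about 0.02 to 0.04 at all drifts with a between-person SD of 2. A visit term alone would not mend that.

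The change is worth making because it is cheap and the trial is small, although the documents cannot show how large the benefit would be.

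**What to change.** In Protocol section 6 and SAP section 3, add visit (1 to 4) as a fixed factor, with participant as the blocking or random factor, to the dose analysis of ET and to the dose main-effect and pairwise comparisons of PP, MP, FI, HR, BLA and RPE. The interaction test and the pre/post jump tests do not need it against a session-wide shift.

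In Protocol section 3, state how dose order is assigned. If sessions have not started, use the four orders of a 4×4 Williams square with four participants each, two men and two women. If they are complete, report the orders actually used and add the visit term, provided that visit order was recorded.

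The cost is 3 residual degrees of freedom, with no extra participants or sessions. If orders were unrestricted random, there is also the loss from non-orthogonality shown in step 6, about 2 points of power when there is no trend.

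### ET in a four-session crossover is to be tested by one-way ANOVA, which ignores that the same participants take every dose; separately, no dose-order scheme or visit-period term is planned

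*Combined protocol and SAP*

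**What the plan says.** Protocol section 3 (Study Design) describes a "Single-blind, randomized, crossover-controlled experimental design" with four conditions (6 g, 4 g, 1 g and placebo), and adds: "Each subject participated in four trials, one for each group". The sample is "16 college students (8 male, 8 female) from Capital University of Physical Education and Sports". No unit of randomisation, set of dose orders or interval between sessions is given. The only restriction on taurine is an entry criterion: "No taurine-based supplementation in the past month".

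The primary objective (protocol section 2) is "To examine the effects of acute pre-exercise taurine supplementation at different doses (6g, 4g, 1g) on RS performance and endurance", so endurance is part of it.

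Protocol section 6 plans "Repeated measures ANOVA (group × time) for performance indicators". SAP section 3 gives as the primary analysis "Repeated measures ANOVA for group × time interaction effects on PP, MP, FI, HR, BLA, and RPE" and, under secondary analysis, "One-way ANOVA for ET across groups". Time in these models is the repeated measurement within a session. Neither document names a term for visit (period) or sequence.

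**The concern.** There are two distinct problems.

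**ET model.** Each participant contributes one ET value under every dose. A one-way ANOVA treats the 64 values (16 × 4) as coming from four independent groups. Stable differences in fitness between men and women, and between individuals, then go into the error, although the crossover was chosen to remove them. A real dose effect on endurance could be missed.

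**Visit period.** Participants repeat a ramp to exhaustion and six maximal sprints in the heat on four occasions, so learning or acclimation across visits is plausible. Without a period term, such a trend stays in the error and, through chance imbalance in order, in the dose contrasts. What follows depends on how orders were assigned, which the documents do not say.

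**Working it through.** The plan gives no power, effect size, SD or drift, so there is no figure to reproduce.

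**From the documents:** 16 participants, 4 sessions each, significance level 0.05, and the tests quoted above.

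**Assumed:** residual (within-participant) SD 1; between-participant SD s = 0.5, 1 or 2; dose effects 0, 0.33, 0.67, 1.0; linear drift d = 0, 0.1, 0.25 or 0.5 per visit; one value per session; dose treated as a within-participant factor in the repeated measures ANOVA.

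**1. ET by one-way ANOVA, no drift.** The noncentrality is 16 × (0.5² + 0.17² + 0.17² + 0.5²) = 16 × 0.5578 = 8.92 in residual-variance units. With a participant term the error has expectation 1 on 45 df, and power is about 66%. Without it, the expected error mean square is [15(1 + 4s²) + 45]/60 = 1 + s², while the dose mean square does not change.

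| s | Error mean square, one-way | Power, one-way | Power, participant term |
|---|---|---|---|
| 0.5 | 1.25 | about 55% | about 66% |
| 1 | 2 | about 25% | about 66% |
| 2 | 5 | about 1% | about 66% |

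The one-way test is conservative here: with no dose effect and no drift it rejects in about 2% of trials at s = 0.5, and in well under 1% at s = 1 or 2. If the effects are doubled (0, 0.67, 1.33, 2), one-way power is about 100%, 97% and 44%, against nearly 100% with a participant term.

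**2. Dose main effect with drift, orders randomised individually.** The difference in visit position between a dose and placebo has variance 2.5 + 2.5/3 per participant, so its mean has SD √((2.5 + 2.5/3)/16) = 0.456 visits. The SE of a contrast is √(2/16) = 0.354. At d = 0.5 the effective SE is √(0.125 + (0.456 × 0.5)²) = 0.421, a rise of 19%. At d = 0.1 and 0.25 the rise is 0.8% and 5%. Simulation, 30,000 trials per cell, participant always in the model:

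| d | Power: random, no period | Power: Williams list with period | Difference (points) | Type I error: random, no period |
|---|---|---|---|---|
| 0 | 66.5% | 65.9% | −0.6 | 5.0% |
| 0.1 | 65.6% | 66.2% | +0.6 | 5.1% |
| 0.25 | 61.2% | 66.4% | +5.2 | 5.1% |
| 0.5 | 50.2% | 66.2% | +16.0 | 4.7% |

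**3. Shared orders.** If four randomly drawn orders are each given to four participants and period is omitted, type I error of the dose test is about 11% at d = 0.25 and 27% at d = 0.5. With a period term it was about 5% in both.

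**4. Group × time interaction.** A constant shift c in one session adds c to every time point of that session. The interaction compares changes within sessions, so c − c = 0. In one simulated data set (4 doses × 6 sprints), adding 0.5 per visit moved the group main-effect F from 0.285 to 0.444 and left the interaction F at 0.619.

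**The case against.** - **The named primary test is largely untouched.** The SAP's primary analysis is the interaction, ET is listed as secondary, and the dose main effect is never named as a test. This stands as far as it goes. But endurance is in the primary objective, and a taurine effect that lifts all six sprints equally would appear only in the main effect.
- **ET may have been meant as a one-way repeated measures ANOVA.** If so, the participant term is present and only the period point remains. The same list uses the repeated measures name for the other outcomes, so the text does not favour this reading.
- **The period gain is small unless drift is strong.** This is correct. The 16-point figure needs 0.5 SD per visit, which is 1.5 SD from first to fourth session. Nor is drift the main problem for ET: as d goes from 0 to 0.5, one-way power moves from 55% to 45% at s = 0.5, from 25% to 22% at s = 1, and from 1.2% to 1.6% at s = 2.
- **Sessions may be over.** The past tense suggests this. The order list and the abstinence rule would then come too late, but the change of model would not.

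A reader might go further and infer any of the following, which the documents do not support:

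- *Dose is confounded with visit and false positives are inflated.* That needs shared or fixed orders. The design is called randomised, and individual randomisation is the natural reading.
- *False positives are safe in any case.* This does not follow either, because no order scheme is stated.
- *The entry-only taurine rule feeds visit trends into the error.* It does not. It leaves outside intake open, which is another mechanism.
- *Carryover biases the results.* No interval or carryover size is given, so this can be neither shown nor dismissed.

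**Conclusion.** The concern holds in two parts of unequal weight.

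The ET test does not fit the design on any reading that takes its name literally. The loss runs from about 11 points of power (66% to 55%) at s = 0.5 to nearly all of it at s = 2, under the assumed effects. It is smaller if effects are large and s is 1 or less.

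The missing period term and order scheme are a conditional weakness. With individually randomised orders the cost is power only, about 0, 1, 5 and 16 points across the assumed drifts. With a few shared orders it becomes inflated type I error. The interaction is affected only if the within-session profile itself changes with visit.

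The taurine rule is a separate minor gap. If outside taurine gave its full effect in a placebo session and added nothing to an active one, use before 1, 2 or 4 of the 16 placebo sessions would shrink the contrast by 1/16 = 6%, 2/16 = 12.5% or 4/16 = 25%. If effects add and use is equal across doses, no shrinkage is expected.

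The sizes rest on assumed SDs, effects and linear drift. The mismatch between the ET test and the design does not. The change should be made; confidence is medium.

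**What to change.** 1. **Model.** Replace the one-way ANOVA for ET with a model containing participant, period and dose. Use the same model, plus within-session time where measured, to test dose main effects for the other outcomes. A mixed model in SPSS does this.
2. **Orders, if sessions are still to run.** Assign from a Williams list, for example P-1-6-4, 1-4-P-6, 4-6-1-P, 6-P-4-1 (grams; P = placebo), with four participants per sequence, two of each sex. Each dose occurs once per visit, and each of the 12 ordered pairs of successive doses occurs once. State the interval between sessions. Always keep the period term with this list: without it, power at d = 0.5 is 43%, below the 50% of random order.
3. **Orders, if sessions are complete.** Report the actual orders and intervals, and fit the model in (1).
4. **Minor and separate.** Extend the no-taurine rule through the last session.

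**Cost.** The period term uses 3 residual df (45 to 42). With the Williams list the contrast variance stays at 0.125 and power falls by less than 1 point at zero drift. If orders were simply random, the variance rises to about 0.134 (+7%). The period term then loses about 3 to 4 points at d = 0 to 0.1, breaks even near √((0.134/0.125 − 1)/(80/48)) = 0.21 SD per visit, and gains about 2 points at 0.25 and 13 at 0.5.

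### For PP, MP and FI the SAP's primary analysis names only the group × time interaction, to which an equal dose effect in every sprint contributes nothing; the dose main effect is not named, and no dose-versus-placebo comparison is planned for any outcome

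*Combined protocol and SAP*

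**What the plan says.** SAP section 1 sets the aim: "Analyze the effects of different taurine doses on RS performance metrics (PP, MP, FI". The protocol's primary objective likewise asks about the 6 g, 4 g and 1 g doses, for sprint performance and for endurance.

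The SAP's primary analysis (section 3, item 3) is "Repeated measures ANOVA for group × time interaction effects on PP, MP, FI, HR, BLA, and RPE". Protocol section 6 is shorter: "Repeated measures ANOVA (group × time) for performance indicators". Neither names a test of dose averaged over sprints.

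Protocol section 5 describes the sprint outcomes as "PP, MP, FI (recorded for each sprint". Section 4, item 4 describes the test as "Six maximal sprints (10 seconds each) with resistance set at 7.5% of body weight". The experimental process in section 3 opens with "Pre-exercise taurine/placebo ingestion (6g, 4g, 1g, or placebo", and the sprints come later, so each sprint in a visit is post-dose.

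The remaining planned tests (SAP section 3, item 4) are "Paired-samples t-tests for reverse vertical jump pre- and post-exercise comparisons" and "One-way ANOVA for ET across groups". The only effect size, in item 5, is partial eta-squared.

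**The concern.** There are two gaps.

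1. **The named test and the objective do not match.** With sprint number as the time factor, the interaction asks whether the sprint-to-sprint profile differs by dose. It does not ask whether a dose moves PP, MP or FI overall. A dose that shifts all six sprints equally, the plainest form of the effect in the objective, is invisible to it.

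2. **No dose is compared with placebo.** The paired t-tests compare before with after, and the ET analysis is a global test without follow-up. A significant global result would not say which dose differs from placebo or by how much. Any comparison added later would be unplanned.

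At stake are a missed uniform effect if the SAP is followed literally, and a choice between main effect, interaction and pairwise tests made after the results are known.

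**Working it through.** The documents give no SD, effect size or power calculation, so there is no planned figure to reproduce.

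**Inputs from the documents.** 16 participants, each taking all four conditions (protocol section 3); six sprints; significance at 0.05 (SAP section 5). Degrees of freedom: dose 3 and 3 × 15 = 45; dose × sprint 3 × 5 = 15 and 15 × 15 = 225.

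**Step 1: the zero, which needs no assumption about variance.** Let the mean for dose j in sprint k be a_k + s_j (an equal shift s_j in every sprint). The interaction term is

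(a_k + s_j) − (ā + s_j) − (a_k + s̄) + (ā + s̄) = 0.

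Numerically, shifts of 0, 0.2, 0.5 and 0.8 (placebo, 1 g, 4 g, 6 g) have mean 0.375 and squared deviations summing to 0.3675. The dose sum of squares is 16 × 6 × 0.3675 = 35.3; the interaction sum of squares is 4 × 10⁻²⁹, which is rounding error.

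**Step 2: size, under assumptions.** Total SD 1; shift d × dose/6; participant share of variance 60%; participant × visit share V of 5%, 15% or 30%; residual E of 35%, 25% or 10%. The dose fractions 0, 1/6, 4/6 and 1 have squared deviations summing to 0.632.

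Main effect, independent sprint errors: noncentrality = 16 × d² × 0.632 / (V + E/6). For d = 0.5 the numerator is 2.528 and the denominators are 0.1083, 0.1917 and 0.3167, giving 23.3, 13.2 and 8.0.

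For AR(1) sprint errors the uncorrected interaction test was simulated with 20,000 runs per setting.

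| d = 0.5 at 6 g, equal in every sprint | V 5% | V 15% | V 30% |
|---|---|---|---|
| Main effect, independent errors | 98% | 84% | 61% |
| Main effect, rho 0.9 | 58% | 56% | 52% |
| Interaction, independent errors | 5.3% | 5.1% | 5.2% |
| Interaction, no shift, independent errors | 4.8% | 4.9% | 5.0% |
| Interaction, rho 0.9 | 10.5% | 10.6% | 10.0% |
| Interaction, no shift, rho 0.9 | 10.0% | 10.0% | 10.6% |

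The interaction rejects no more often with the shift than without it. The excess over 5% at rho 0.9 comes from non-sphericity, not from the dose.

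**Step 3: where the interaction is the better test.** Let the shift grow from zero at sprint 1 to twice its mean at sprint 6 (weights 0, 0.4, 0.8, 1.2, 1.6, 2; squared deviations sum to 2.8), mean 0.3 SD at 6 g. Interaction noncentrality = 16 × 0.09 × 0.632 × 2.8 / E = 7.3, 10.2 and 25.5.

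| Growing shift, mean 0.3 SD | V 5% | V 15% | V 30% |
|---|---|---|---|
| Main effect, independent errors | 64% | 39% | 24% |
| Interaction uncorrected, independent errors | 31% | 44% | 91% |
| Interaction Greenhouse-Geisser, independent errors | 15% | 24% | 78% |
| Main effect, rho 0.7 | 30% | 26% | 22% |
| Interaction Greenhouse-Geisser, rho 0.7 | 32% | 47% | 92% |

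**Step 4: 6 g versus placebo.** Paired t on the six-sprint mean, 15 df, noncentrality d / √(2(V + E/6)/16) = 4.30, 3.23 and 2.51 at d = 0.5. At rho 0.9 the factor 1/6 is replaced by the mean of the 6 × 6 correlation matrix, 29.66/36 = 0.824.

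| 6 g versus placebo, d = 0.5 | V 5% | V 15% | V 30% |
|---|---|---|---|
| Unadjusted, independent errors | 98% | 86% | 65% |
| Holm first step (0.05/3), independent errors | 93% | 70% | 45% |
| Unadjusted, rho 0.9 | 62% | 60% | 57% |
| Holm first step, rho 0.9 | 42% | 40% | 37% |

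**Step 5: error rates of a remedy.** With no dose effect, at least one Holm contrast rejects in 4.2% to 4.8% of runs. If a claim may rest on either the main effect or a Holm contrast, the rate is about 7% per outcome. Over PP, MP, FI and ET at 5% each it is 1 − 0.95⁴ = 18.5% if independent and 4 × 5% = 20% at most.

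**The case against.** The best defence is protocol section 6. Its notation is the usual shorthand for a two-factor model, and such a model yields the dose main effect as a matter of course. That stands as a possible reading, and it limits the first gap: the main effect would be available but not designated. It does not touch the second gap.

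The interaction is also a reasonable question. The protocol background presents fatigue as a target of taurine, the sprints are separated by only 10 seconds, and step 3 shows the interaction winning under some patterns. This stands too. The documents do not say which pattern or correlation to expect, so they support adding the main effect but do not settle that it must rank first.

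A reader might infer that the plan cannot detect any dose effect. The documents do not support that: an effect that changes across sprints can reach the interaction, and ET has a global test that includes placebo. Nor does the interaction argument carry over to HR, BLA and RPE. These are measured before exercise as well as after, and may include a pre-dose value; with one, an effect equal at all later times would appear in the interaction.

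**Conclusion.** The concern holds in this form. For PP, MP and FI the only effect named in the primary analysis is one to which an equal dose effect across sprints contributes exactly nothing. Under the more generous reading of protocol section 6, the test that would see such an effect is produced but given no role. Under either reading no dose-versus-placebo comparison is planned for any outcome.

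The zero is algebraic and rests only on time being sprint number with every sprint post-dose. All power figures are illustrative: they depend on the assumed variance shares, a linear dose effect and the sprint correlation, none of which the documents give.

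This should be fixed before analysis. It falls short of a defect that invalidates the plan, because one of the two readings already contains the main effect and the interaction answers a legitimate question.

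**What to change.** 1. For PP, MP and FI, add the within-subject dose main effect (mean over six sprints) as a named test of the overall dose effect. Keep dose × sprint as a named test of the fatigue profile, with a Greenhouse-Geisser correction. State before analysis which of the two carries the primary conclusion.
2. Pre-specify 6 g, 4 g and 1 g versus placebo as within-subject contrasts, with mean differences, 95% confidence intervals and Holm adjustment. Choose one decision rule: either the Holm contrasts alone carry the dose claims, or they are tested only if the main effect is significant.
3. For ET, replace the one-way ANOVA with a repeated-measures dose test and the same three contrasts.

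**Cost.** No new data are needed. Items 1 and 2 use the repeated-measures layout already planned, with added contrasts; item 3 changes the model and is not a matter of wording. Downsides to state in the SAP:

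- Holm lowers power for 6 g versus placebo, as step 4 shows.
- Greenhouse-Geisser is conservative with 16 participants and 15 interaction degrees of freedom: it rejects in 1.2% to 3.2% of runs with no profile effect.
- Holm protects the contrasts within one outcome only. Name one primary outcome, or disclose the 18.5% to 20% across four.

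Dose comparisons for jump height, HR, BLA and RPE serve secondary objectives and are not part of this change. The protocol describes participation in the past tense. If data have been seen, date and disclose the amendment.
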